3.3 Exclusion Criteria

Patients that meet any of the criteria listed below will not be eligible for study entry:

- Prior exposure to Radium-223
- Received an investigational therapy within the 4 weeks prior to registration, or is scheduled to receive one during the treatment period
- Received a new anti-cancer agent within 4 weeks prior to registration
- Received external beam radiotherapy within 4 weeks prior to registration
- Received systemic therapy with radionuclides (e.g. strontium-89, samarium-153, rhenium-186 or rhenium-188) for the treatment of bone metastases
- Treatment with cytotoxic chemotherapy within 4 weeks prior to registration
- Symptomatic nodal disease, i.e. scrotal, penile or leg edema.
- Visceral metastases (including cerebral metastases) from CRPC (>2 lung and/or liver metastases [size $\geq 2\text{cm}$]; Lymphadenopathy exceeding 6 cm in short-axis diameter or any

Radium-223

MSKCC

size pelvic lymphadenopathy if it is thought to be a contributor to concurrent hydronephrosis), as assessed by CT, MRI or chest X-ray within the 8 weeks prior to registration

PCCTC LOI: c13-124

IRB#: 14-098 A (5)

- Concurrent chemotherapy. Patients may be on other non-chemotherapy anti-cancer treatments, per FDA labeling of Radium-223, provided that these are not changed during the primary pain assessment period
- Major surgery within 30 days prior to registration
- Imminent spinal cord compression based on clinical findings and/or magnetic resonance imaging (MRI). Treatment should be completed for spinal cord compression.
- Patients with a, “currently active,” second malignancy other than non-melanoma skin cancers or non-invasive bladder cancers or other in-situ or non-invasive malignancies. Patients who have completed therapy for a prior malignancy and are free of disease for ≥ 3 years are eligible.
- Any other serious illness or medical condition, such as but not limited to:
 - Any infection \geq National Cancer Institute Common Terminology Criteria for Adverse Events (NCI-CTCAE) version 4.0 Grade 2
 - Cardiac failure New York Heart Association (NYHA) III or IV
 - Crohn’s disease or ulcerative colitis
 - Bone marrow dysplasia
 - Fecal incontinence
- Any other condition which, in the opinion of the Investigator, would make the subject unsuitable for trial participation

4. PATIENT REGISTRATION AND ENROLLMENT PLAN

4.1 Enrollment Plan

4.1.1 Participating Study Centers

This study is anticipated to be conducted at 3 sites.

4.1.2 Recruitment

Potential research subjects will be identified by a member of the patient's treatment team, the protocol investigator, or research team at participating centers from Medical Oncology, Radiation Oncology and Urology offices. Investigators will screen the patient's medical records for suitable research study subjects and discuss the study and their potential for enrolling in the research study.

4.2 Registration Procedure

After eligibility screening and confirmation that a patient is eligible, patients who are selected to participate will be registered with the PCCTC Caisis EDC, the PCCTC Clinical Data Management System (CDMS). A record of patients who fail to meet eligibility criteria (i.e., screen failures) will be maintained. Patient registration must be complete before beginning

Radium-223

MSKCC

PCCTC LOI: c13-124

IRB#: 14-098 A (5)

any treatment or study activities. A complete, signed study consent and HIPAA authorization are required for registration.

4.2.1 PCCTC Registration:

Confirm eligibility as defined in Section 3 Patient Selection.

Obtain informed consent, by following procedures in Section 11.4 Written Informed Consent

Obtain completed or partially completed protocol specific Eligibility Checklist.

All participants will be registered through PCCTC Caisis EDC, the PCCTC's CDMS.

To complete registration and enroll a participant, the study staff at that site must contact the designated research staff at PCCTC to notify him/her of the participant registration. The site staff then needs to email registration/eligibility checklist and source documents to the PCCTC at [contact]. (Note: Source documentation of eligibility is not required for MSKCC participants.)

Radium-223

MSKCC

PCCTC LOI: c13-124

IRB#: 14-098 A (5)

These documents must be sent for each enrollment within 24 hours of the informed consent form being signed.

Upon receipt, the research staff at PCCTC will conduct an interim review of all documents for all non-MSKCC participants. If the eligibility checklist or source documentation is missing, the patient will be registered pending enrollment and the site is responsible for sending the completed registration documents within 30 days of the consent.

If the external registration submission is complete, the participating site IRB has granted approval for the protocol, and the site has been activated by MSKCC, PCCTC will register the non-MSKCC participants. MSKCC participants will be fully registered by MSKCC.

Once the participant is registered, the participant will be assigned a PCCTC Caisis Subject ID. This number is unique to the participant and must be written on all data and correspondence for the participant. This PCCTC Caisis Subject ID will be relayed back to study staff at the registering site via e-mail and will serve as the enrollment confirmation.

4.2.2 *Institutional Registration*

Patient registration at each study site/institution will be conducted according to the institution's established policies. Patients must be registered with PCCTC, MSK and their local site/institution before beginning any treatment or study activities.

At MSKCC, all participants must be pended with MSKCC's Protocol Participant Registration (PPR) Office prior to submitting registrations to PCCTC.

PCCTC will register all non-MSKCC participants with MSKCC's Protocol Participant Registration Office (PPR) per MSKCC's guidelines.

MSKCC will register all MSKCC participants with MSKCC's Protocol Participant Registration Office (PPR) per MSKCC's guidelines.

Radium-223
MSKCC**5. TREATMENT/INTERVENTION PLAN**

The following assessments and procedures will occur during the study. A schedule of assessments is shown below.

	Screening Period		Treatment Period												Follow up visit (visits occur every 3 months +/- 1 week) ^{eg}
	Week -4 ^a	Wk1 (within 5 days after the run-in period ends)	Wk4	Wk5	Wk8	Wk9	Wk12	Wk13	Wk16	Wk 17	Wk20	Wk21	Wk24	Wk25/ Safety FU	
	Run-in Period														
Ra-223		X		X		X		X		X		X			
Informed consent	X														
Eligibility criteria/ Demographics / Medical history	X														
Testosterone level	X														
Imaging assessments ^b	X							X						X	X
Physical exam	X		X		X		X		X		X		X		X
Vital signs	X		X		X		X		X		X		X		X
Performance status	X		X		X		X		X		X		X		X
Clinician reported			X-----X												

Radium-223
MSKCC

adverse events															
Concomitant meds	X		X-----X												
ECG	X		As clinically indicated												
Pain scale (BPI Short Form using a PRO instrument x7days)		X ^f		X	X	X	X	X	X	X	X	X	X	X	X
Fatigue scale (BFI item using a PRO instrument x7days)		X		X	X	X	X	X	X	X	X	X	X	X	X
Analgesic diary ^h		X		X	X	X	X	X	X	X	X	X	X	X	X
Hematology ^c	X		X	X	X	X	X	X	X	X	X	X	X	X	X
Serum biochemistry ^d	X		X	X	X	X	X	X	X	X	X	X	X	X	X
PSA	X		X	X	X	X	X	X	X	X	X	X	X	X	X
Bone markers	X					X	X								

Abbreviations: BFI=Brief Fatigue Inventory; BPI=Brief Pain Inventory; CT=computerized tomography; ECG=electrocardiogram; MRI=magnetic resonance imaging; PSA=prostate-specific antigen.

^a Informed consent must be obtained, and radiologic assessments will be obtained within 4 weeks of study start date.

^b Imaging assessments will be performed every 12 weeks \pm 1 week. Bone scan, FDG PET (FDG will be done in consenting patients and is considered optional), CT scan or MRI of the abdomen and pelvis and CT scan of the chest or Chest X-ray

^c Hematology: White blood cells count (WBC), red blood cell count (RBC), hemoglobin (HGB), hematocrit (HCT), platelet count (UNVPLT), neutrophils (NEUTP), lymphocytes (LYMP), monocytes (MONP), eosinophils (EOSP), basophils (BASOP)

^d Serum biochemistry: calcium (CA), albumin (ALB), total protein (TP), sodium (NA), potassium (K), chloride (CL), blood urea nitrogen (BUN), creatinine (CREAT), alkaline phosphatase (ALK), alanine transaminase (ALT), aspartate transaminase (AST), total bilirubin (TBILI), lactate

dehydrogenase (LDH), gamma-glutamyl transpeptidase (GGT), phosphate (PHOS), magnesium (MG), glucose (GLU), carbon dioxide (CO2)

- ^e Subjects should be followed up every 3 months following the safety follow-up visit for a total of 2 visits or until initiation of another therapy and be assessed for any potential long term toxicity as well as key efficacy parameters
 - ^f Subjects will indicate their daily pain score for 7 days during the 28 day screening period to establish that their average baseline pain score is ≥ 3 as measured for 4 of 7 days.
 - ^g During the follow-up period, subjects will answer questions on the BPI and BFI as well as enter information on their analgesic dairy for at least 4 of 7 days prior to their scheduled follow up visit
 - ^h Subjects will update their analgesic dairy daily during the run-in period and daily during the pain assessment periods throughout the trial
-

5.1 Screening/Pretreatment Assessment (Day -28 to Day -1)

Before initiating any screening activities, the scope of the study should be explained to each patient. Patients should be advised of any known risks inherent in the planned procedures, any alternative treatment options, their right to withdraw from the study at any time for any reason, and their right to privacy. After this explanation, patients should be asked to sign and date a research authorization/HIPAA form and an IRB-approved statement of informed consent that meets the requirements of the Code of Federal Regulations (Federal Register Vol. 46, No. 17, January 27, 1981, part 50).

The screening visit will determine patient eligibility according to the inclusion and exclusion criteria. The following assessments will be performed at this visit:

- Obtain informed consent and research authorization
- Record demographics (including age) and medical history (including prior treatment for prostate carcinoma)
- Physical exam
- ECOG performance status
- Vital signs [body temperature, blood pressure, pulse, respiratory rate, weight, height]
- Obtain histologic and radiologic confirmation of disease
- Confirm eligibility according to the inclusion/exclusion criteria
- Perform laboratory tests [hematology, serum biochemistry, PSA, testosterone level, bone markers]
- ECG
- Baseline imaging assessments: Bone scan, FDG PET (in consenting patients at centers that agree to perform FDG PET scans), CT scan or MRI of the abdomen and pelvis and CT scan of the chest or Chest X-ray]

Relevant information should be documented. The institutional registration should be finalized, and appropriate documents (i.e., signed informed consent, research authorization/HIPAA form, and supporting source documentation for eligibility questions) emailed to the lead site/sponsor.

Information for patients who do not meet the eligibility criteria to participate in this study (i.e., screening failures) should be captured in consortium database at the pretreatment assessment.

5.1.1 *Run-In Period (Day -7 to Day -1 +/- 5 days)*

During the Run-In Period, subjects will self-report pain and fatigue using a PRO instrument daily for 7 days and record analgesic medication information on a paper pain medication diary to establish that their BPI average baseline pain score is ≥ 3 as measured for a minimum of 4 of the 7 days (See Appendix I for instructions). This data will be used to confirm eligibility based on pain experience. Upon confirmation of eligibility, the subject's registration will be completed and the subject must start treatment within 5 days of registration.

Radium-223

MSKCC

PCCTC LOI: c13-124

IRB#: 14-098 A (5)

If run-in requirements are not met with respect to pain score, subjects may be eligible to rescreen at a later time.

5.2 Treatment/Intervention Period (Week 1, Day 1 to Week 25, Day 169 (treatment visits have a window of ± 3 days))

Unless otherwise specified, all visit procedures are to be performed prior to Radium-223 administration on the day of the visit. Radium -223 will be administered every 4 weeks for 6 doses at a dose of (50 kBq (0.00135 mCi) (55kBq (.0015 after NIST update) Because ALSYMPACA did not assess radiographic assessments during treatment, neither radiographic progression nor PSA progression should be used to discontinue treatment. However, patients are *permitted, per FDA labeling*, to be maintained on other anti-cancer therapies in addition to Radium-223 provided that these are not changed in the midst of pain assessments. Other-cancer therapies must be initiated 4 weeks prior to the run-in period. Patients with an increase in pain of 2 points on their BPI worst pain item compared to baseline and confirmed at least 2 weeks later will be considered to be treatment failures and will be taken off trial. In the absence of clinical progression, patients will continue to receive all six treatments, and will continue treatment until clinical progression, unacceptable toxicity, or any criteria in Section 5.6 Removing Patients from the Protocol. Patients will return to the clinic every 4 weeks for the following assessments:

- Physical exam
- ECOG performance status
- Vital signs [body temperature, blood pressure, pulse, respiratory rate, weight]
- ECG (as clinically indicated – not required at every visit)
- Lab tests [hematology, serum biochemistry, PSA, bone markers (to be done at the Wk 9 and Wk 13 visit)]
- Clinician reported adverse events and concomitant medications will be monitored continuously throughout the study
- Imaging assessments will be performed every 12 weeks \pm 1 week during treatment period (Week 13, Week 25 [Safety Follow-Up Visit]): Bone scan, FDG PET (in consenting patients at participating centers), CT scan or MRI of the abdomen and pelvis and CT scan of the chest or Chest X-ray]
- During the treatment period, as outlined in the table above, subjects will self-report information on pain, fatigue and health-related quality of life via a PRO instrument (See Appendix I for instructions). Data will be entered by the subject daily during the 7 day reporting period according to the scheduled outline in the above table. Subjects will also update their analgesic dairy during this 7 day period as well. All PRO entries should be done at home prior to visits to the clinic for either regularly scheduled visits or imaging appointments. If for any reason PRO entries are done while the subject is at the clinic, the staff should not provide any input or assistance other than technical help on using the system.

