8.2 Secondary endpoints

- Bone-ALP response will be described as:
 - Percentage of change from baseline to 12 weeks (or earlier for those who discontinue study therapy)
 - Maximum change (rise or fall) in bone-ALP during the treatment period reported for each patient as a waterfall plot
- Changes in total-ALP will be defined as for bone-ALP above
- PSA decline will be reported on all patients. Using PCWG2 guidelines ¹, the percentage of change in PSA from baseline to 12 weeks, as well as the maximum decline in PSA will be reported for each patient using a waterfall plot.
- Progression, for those patients showing an initial decline in PSA from baseline, is defined as an increase in PSA that is $\geq 25\%$ and ≥ 2 ng/mL above the nadir, and which is confirmed by a second value 3 or more weeks later (i.e., a confirmed rising trend).
- Progression, for those patients with no decline in PSA from baseline, is defined as an increase in PSA that is $\geq 25\%$ and ≥ 2 ng/mL after 12 weeks. Note: PSA progression as such will not lead to study discontinuation
- Time to First Radiographic or Clinical Progression (TTFROCP) based on RECIST version 1.1 and Prostate Cancer Working Group 2 (PCWG2) definitions
- Changes in other bone markers:
 - Serum C-telopeptide (sCTX-1)
 - N-terminal propeptide of procollagen type 1 (PINP)
- Radiographic response through the RECIST criteria 1.1 will also be determined using FDG PET/CT to assess for treatment effect in bone.
- Time to pain progression, defined as time until a ≥ 2 point increase in pain compared to baseline confirmed at least 4 weeks later.
- Change in analgesic use assessed by the WHO analgesic ladder
- Changes in measure of tiredness measured by the worst fatigue item (item #3) from the Brief Fatigue Inventory.
- Measures of pain interference specifically evaluating its affect on general activity and sleep as assessed on BPI
- Evaluate the short and long term toxicity to treatment

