10.1.2 Analysis of secondary endpoints

A summary of adverse events will be tabulated at baseline and during treatment. Analgesic use will be tabulated, converted into equivalent units, and changes in opiate equivalents before and after treatment will be compared. Descriptive statistics will be used to report the proportion of patients with changes in fatigue scores compared to baseline according to the worst fatigue item (Item #3) of the Brief Fatigue Inventory, at weeks 8 and 12. Descriptive statistics will also be used to report the proportion of patients with changes in pain interference scores compared to baseline based on the interference with activities item of the BPI, at weeks 8 and 12.

The time to radiographic progression and pain progression will be summarized using the cumulative incidence function. The percent change in PSA and bone turnover markers from baseline to 12 weeks will be summarized with descriptive statistics. Longitudinal assessments of BPI, and tiredness will be recorded and summarized over time.

Radiographic progression using PCWG2 criteria for bone scans, and RECIST for soft tissue/measurable disease will be used. The use of FDG PET imaging to demonstrate post-treatment effects is exploratory in nature – the impact of radium on the actual cancer cell is not known. Furthermore, there is no standard method for assessing post-treatment FDG PET changes that have been prospectively validated in prostate cancer. Because Ra-223 is a bone directed agent, bone lesions will be treated separately from soft tissue lesions. We will therefore examine multiple methods of examining post-treatment changes in FDG PET in order to explore which of those will most closely correlate with both pain response. These will include:

- A. We will analyze up to 5 bone lesions. Analysis will be performed either on HERMES or AWS workstation. For each lesion, a five point confidence scale will be employed as follows: 1: negative for tumor; 2: probably negative for tumor; 3: equivocal for tumor; 4: probably positive for tumor; 5: definitely positive for tumor. The SUV for each lesion will also be recorded along with its location.

Radium-223

MSKCC

PCCTC LOI: c13-124

IRB#: 14-098 A (5)

SUVpeak lean body mass will be determined in each of these lesions. The sum of these values at baseline will be compared to that of the sum at followup.

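### Bone markers have only a screening baseline, up to 28 days before the first dose, so their reported 12-week change can include untreated time

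*Combined protocol and SAP*

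**What the plan says.** The pre-treatment bone-marker sample belongs to the screening visit. Under the heading "5.1 Screening/Pretreatment Assessment (Day -28 to Day -1", the list of screening procedures includes "Perform laboratory tests [hematology, serum biochemistry, PSA, testosterone level, bone markers".

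During treatment, Section 5.2 asks for "Lab tests [hematology, serum biochemistry, PSA, bone markers (to be done at the Wk 9 and Wk 13 visit". The week restriction attaches to the bone markers; hematology, biochemistry and PSA carry none.

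Section 8.2 makes bone-ALP change from baseline to 12 weeks (earlier for patients who stop therapy) and its maximum change secondary endpoints, and adds changes in CTX and PINP. Section 10.1.2 sets the analysis: "The percent change in PSA and bone turnover markers from baseline to 12 weeks will be summarized with descriptive statistics".

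For pain, Sections 8.1 and 10.1.1 define the baseline exactly: an average over 7 pretreatment days with at least 4 completed. Nothing comparable defines baseline for any laboratory value.

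**The concern.** With no control arm, change from baseline is all the evidence the trial will have on Objective 2.2.1, the effect on bone turnover. Section 1.3.3 describes these markers as altered by Radium-223 more than PSA is, so they are the main laboratory readout. If the baseline is drawn weeks before the first injection, whatever the marker does before treatment is added to what it does on treatment, and the summary cannot separate the two. The gap also differs between patients, so the same reported percentage covers different amounts of untreated time.

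**Working it through.** The plan states no figure for this point. The only operating figures it gives belong to the primary design; exact two-stage calculation (27 then 36 patients, at least 6 then at least 17 responders) gives 0.09995 and 0.902 against the stated 0.10 and 0.90. They reproduce and do not depend on bone markers.

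**1. Is there any Day 1 bone-marker sample?** Section 5.1 places the draw at screening; Section 5.2 names only Weeks 9 and 13. In the text form of the Section 5 schedule table the columns cannot be aligned with certainty, but neither plausible alignment puts a bone-marker mark at Week 1: one gives Week -4, 9 and 12, the other Week -4, 8 and 9. The finding rests on the prose and the table does not contradict it.

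**2. How long is the untreated part?** Let g be the days from the screening draw to dose 1. Section 5.1 allows g from 1 to 28. Nominal days from dose 1 are (13 - 1) × 7 = 84 to the Week 13 visit and (9 - 1) × 7 = 56 to the Week 9 visit. Visit windows are ignored. Untreated share = g / (g + days on treatment):

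| g | to Week 13 | to Week 9 |
|---|---|---|
| 28 | 28/112 = 25% | 28/84 = 33% |
| 7 | 7/91 = 7.7% | 7/63 = 11% |
| 1 | 1/85 = 1.2% | 1/57 = 1.8% |

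Section 5.1 lists consent and the laboratory tests at the same visit and then describes a 7-day run-in. A gap of a week or more is therefore the likelier sequence, though the text does not require it.

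**3. What does the gap do to the result?** Let T be the true proportional change from Day 1 and d the proportional drift from screening to Day 1. The reported change is R = (1 + T)(1 + d) - 1. For an illustrative true fall of 20%, R = 0.8(1 + d) - 1 = -0.20 + 0.8d. A positive d hides part of the fall; a negative d enlarges it.

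**4. What is d?** The documents do not say. Two features pull in opposite directions:

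- Section 3.2 requires progressive disease, shown by rising PSA or by new lesions on bone scan. Markers might be rising, but no entry criterion concerns turnover markers.
- Section 5.2 lets other anti-cancer therapy continue if begun 4 weeks before the run-in. With the run-in nominally starting on Day -7, that start can be as late as Day -35. A Day -28 sample then falls 35 - 28 = 7 days after it, and any early fall due to that therapy up to Day 1 is credited to Radium-223. Section 5.7 also lets bisphosphonates or denosumab continue.

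The possible untreated time can be stated; the resulting error cannot.

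**The case against.** The strongest reply is that this is small. The endpoints are secondary, descriptive and untested, 28 days is the maximum, and a draw close to dosing leaves almost no gap. All of that stands and limits the weight of the point, but it does not supply a Day 1 sample or a definition of baseline.

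A reader might go further and infer that PSA and total ALP also lack a Week 1 sample. The documents do not support that. Section 5.2 is headed as starting at Week 1, Day 1, states that "all visit procedures are to be performed prior to Radium-223 administration on the day of the visit", and lists PSA and biochemistry without naming weeks. The phrase "Patients will return to the clinic every 4 weeks for the following assessments" leaves some doubt whether Week 1 counts as a return visit, but doubt is not omission. The table does not settle it. It has a column headed "Wk1 (within 5 days after the run-in period ends" and a run-in heading whose position is lost in the text form. The dosing and imaging rows fit if the run-in has no column of its own. The physical-examination and vital-sign rows match the prose only if it has one, and that alignment would mark PSA at Week 1.

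A reader might also infer that PSA progression could be partly met before treatment. The rule beginning "Progression, for those patients with no decline in PSA from baseline, is defined as an increase in PSA that is" requires at least 25% and at least 2 ng/mL after 12 weeks, so it cannot be met before a dose; patients with an initial decline are judged from nadir. Nor can the error be assumed to run against Radium-223, for the reasons in step 4.

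**Conclusion.** The point holds for bone-ALP, CTX and PINP. Their only planned pre-dose value comes from screening, so up to 28 days, at most a quarter of the nominal interval to Week 13, can precede any Radium-223. The resulting error has unknown size and sign and varies with each patient's delay. This assumes that the prose of Sections 5.1 and 5.2 governs and that the Week 13 visit supplies the 12-week value.

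For PSA and total ALP the conclusion is narrower: baseline is undefined, so if both screening and Week 1 values exist, nothing says which is used. The primary pain endpoint, the 27/63 design and treatment decisions are unaffected. This is a worthwhile low-cost improvement, not a flaw that threatens the trial's main conclusion.

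**What to change.** Move the bone-marker baseline draw from the screening visit to Week 1 Day 1, before injection, in Section 5.1, Section 5.2 and the schedule table. Bone markers are not an eligibility test, so no enrollment decision waits on them and the number of samples per treated patient is unchanged.

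In Section 8.2, define the laboratory baseline as the last value before the first dose. The same sentence settles which PSA and total-ALP value is used.

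The cost is a small schedule edit and one sentence. The drawback is that a missed Day 1 draw would leave that patient without a bone-marker baseline; keeping the screening draw as a backup avoids this at the price of one extra sample. The change removes only the drift before dose 1. Any effect of permitted concomitant therapy after Day 1 remains mixed with that of Radium-223, as it must in a single-arm design.
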